D.9.6. Future developments in HCV treatment. Study participants will receive state-of-the-art treatment (IFN in combination with telaprevir and ribavirin). As additional regimens become available with either more convenient dosing, fewer side effects, or increased efficacy, participants in all 3 arms will receive treatment according to best available practices. On October 10, 2014, the FDA approved fixed-dose (ledipasvir and sofosbuvir). Because rates of SVR are >95% in patients initiating treatment with fixed-dose (ledipasvir and sofosbuvir), all newly enrolled subjects will initiate treatment with this regimen. It is likely that our intensive models of care will be generalizable to IFN-sparing regimens which include only oral therapies. We recognize that HCV treatment has been greatly simplified, but issues with adherence, resistance, side effects, and cost will remain.

D.10. Data sources and collection.

D.10.1. Overview. Sources of data will include: blood and urine tests, participant interviews, medical charts, staff activity and expense logs, direct observation of staff, and electronic adherence monitors (Table 3).

D.10.2. Research visits. Research visits will occur at baseline, then every 4 weeks during the first 12 weeks of treatment, then at week 24 (if necessary), a “Final Treatment Week visit” will be conducted after the last day of treatment, and then post-treatment visits after 4, 12, and 24 weeks, for a total of up to 9 research visits. Participants will receive \$25 for each visit and an additional \$20 for visits with blood draws.

Baseline visit (Table 3). At baseline we will assess: sociodemographic and HCV clinical factors, potential mediating variables based on the IMB model, potential moderators (including psychiatric status, substance use, and unstable housing), and additional psychosocial factors hypothesized to predict adherence. The baseline visit will take approximately 3 hours. Blood will be collected at the first visit and stored for possible HCV viral load and resistance testing, and for future studies.

Follow-up visits (Table 3). Follow up visits will occur at weeks 4, 8, 12, and 24 (if necessary).

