Adherence to all medications will be evaluated by electronic monitors and self-report. Weeks on treatment will be determined by electronic monitors and chart review. HCV viral load, virological endpoints, and resistance results will be obtained by chart review and blood draw, if unavailable by chart review. IMB model mediators will be assessed at weeks 8 and 12. Potential moderators will be assessed at each monthly visit.

Table 3. Overview of Data Collection by Aims

Aim & Hypothesis	Construct	Measure, source	Research visit (week)	Source
Outcome Measures				
Aim 1, H1	Adherence	Med-ic® and MEMS® Electronic Monitors	4,8,12	Electronic
Aim 1, H2	Completion	Medical record	NA	Chart
Aim 1, H3	Viral load (SVR)	HCV VL by Roche TaqMAN assay	0,4,8,12, 24, FU 4, FU12, FU24	Chart, Blood
Aim 1/2, H4	Resistance	HCV GenoSURE NS3/4A, NS5A, NS5B (Monogram)	4, 8, 12, 24, FU4, FU12, FU24	Chart, Blood
Aim 3	Cost	HCV treatment mDOT and CGT interventions Non-HCV treatment health services	NA NA 12,24, FU4, FU12, FU24	Chart Logs, Direct Observation Q
Other covariate measures*				
All	Demographics	Age, race/ethnicity, education, income, housing	0	Q
All	HCV-related clinical information	HCV VL, HIV, HCV genotype/subtype, IL28B, APRI and FibroSURE (biomarkers of liver fibrosis)	0	Chart
All	Substance use	Addiction severity Index-Lite (ASI-lite) (152,153) Alcohol use (AUDIT) (154) Urine toxicology EMIT assay	0,4,8,12, 24, FU4, FU12, FU24	Q, Urine
All	Methadone dose opiate withdrawal	Methadone dose; Subjective and Objective Opiate Withdrawal Scales (SOWS and OOWS) (155)	0,4,8,12, 24, FU4, FU12, FU24	Q
All	Neuropsychiatric	MINI (138-140)	0	Q
All	Information, motivation, and behavioral Skills	Health Beliefs Model (161) HCV Motivation (161) Adherence Self-Efficacy (161)	0, 12	Q
All	Social support	Medical Outcomes Scale (162)	0,4,8,12,24, FU4, FU12, FU24	Q
All	DAA levels	GC-MS (if additional funding obtained)	4	Blood
All	Depression, anxiety, and hostility	Depressive symptoms (BDI-II) (156-157) Brief Symptom Inventory (BSI) anxiety subscale (158) BSI hostility subscale (158-160)	0,4,8,12,24, FU4, FU12, FU24	Q
All	Psychosocial factors	Stages of readiness for HCV treatment (183) Trust in physician (184)	0 0,4,8,12,24, FU4, FU12, FU24	Q
All	Quality of life	HCV QOL and EQ-5D (163-166)	0,4,12, 24, FU4, FU12, FU24	Q
All	Med side-effects	Adult ACTG adherence instrument – revised (167)	0,4,8,12, 24, FU4, FU12, FU24	Q

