using prevailing national wage rates to determine the cost of the time, and applying this cost to each DOT interaction. Patient time costs will be valued based on the minimum wage, because most patients are likely to be unemployed. The cost of the CGT intervention will be similarly determined through observational studies, as well as staff member time and activity logs, and expense logs will be maintained for transportation and other incidental costs. Provider time spent on research activities, such as conducting research visit assessments, will be excluded. We will also examine the cost of health care services received outside of the study (emergency department visits, hospitalizations, substance abuse treatment) based on quarterly patient self-reports.

D.10.4. Data Sources. There will be 6 data sources. Results will not be provided to participants' medical providers unless participants specifically request (in writing) that study staff release this information.

Medical record. HCV viral load and resistance assays (if no SVR) will be obtained when possible by chart review. HCV viral load is measured by the Roche TaqMAN assay and HCV resistance is measured by the Monogram HCV GenoSURE NS3/4A assay, which is automatically run on any HCV viral load which is ≥ 2000 IU/ml. Information on treatment interruptions and discontinuation will be obtained from medical records.

Blood. Three tubes of blood will be drawn at weeks 0, and 4, and stored at Einstein's Clinical Research Center (CRC). HCV viral load and resistance assays will be performed if not available by chart review. For subjects who fail to achieve SVR, resistance testing will be performed on post-treatment specimen. All testing will be performed at Montefiore's laboratories.

Urine toxicology. Participants will provide urine specimens at each research visit, which will be tested for cocaine and opiates (and pH to ensure validity) using enzyme multiplied immunoassay technique.

Adherence by electronic monitors (Med-ic® and MEMS®) and self-report.

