For the analysis of repeatedly measured adherence (using 6 post-baseline time points and adherence as a continuous measure), we will apply mixed effects linear model to test if the 3 groups are significantly different. This model accounts for within-subject longitudinal outcome correlation by taking the subject-level intercept as random. The model will include potential confounding variables. If the omnibus equality test is rejected, we will conduct the 2 post-hoc pairwise tests described above. Concerning potential clustering effects in the CGT arm, we used pilot data (5 groups) to examine whether clustering influenced adherence. Between cluster variation was not significant, as tested by application of a random effects repeated-measure ANOVA model. Clustering in the GCT arm will be minimal, and we will not adjust for it in statistical or power analysis.

We will also apply mixed effects logistic regression to test the significance of mDOT and CGT on repeatedly-measured undetectable HCV VL throughout the intervention period, adjusting for substance use. Changes in illicit drug use will be analyzed using urine toxicology data from each visit, counting the “person-month” as a unit of analysis, and analyzing the proportion of person-months that are positive for use of illicit drugs using a chi-square analysis.

As secondary analyses, we will examine if mDOT and CGT effects, v. TAU, will be mediated by IMB components. We will assess IMB model mediators of adherence at baseline, and during the intervention, and will analyze changes in those variables from the baseline to the intervention period. The indirect effects of IMB mediators will be tested by assessing changes in coefficients of the intervention effect (mDOT or CGT) with and without IMB component(s) in mixed effects models. Confidence intervals of the mediated effects will be calculated by bootstrapping, and mediation assumed if confidence intervals do not include zero.

D.12.3. Hypotheses for Aim 2. We hypothesize that only a minority (~20%) of IDUs will develop resistance, and that the relationship between adherence and resistance will be quadratic.

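### The drug-use analysis appears to count the pre-treatment urine as an outcome and cannot adjust for it; D.12.2 should name the arm contrast, use post-baseline urines and adjust for week 0

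*Combined protocol and SAP*

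**What the plan says.** Section D.12.2 (Analytic plan for Aim 1) states: "Changes in illicit drug use will be analyzed using urine toxicology data from each visit". Each unit in that analysis is one month of one participant's time, so a participant contributes several. The test itself is set out as "analyzing the proportion of person-months that are positive for use of illicit drugs using a chi-square analysis". The section names no arms, no covariate and no restriction on visits for it.

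The visits are defined elsewhere:

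- D.10.4 (Urine toxicology): "Participants will provide urine specimens at each research visit".
- D.10.2: "Research visits will occur at baseline, then every 4 weeks during the first 12 weeks of treatment", and then later visits, up to 9 in all.
- Table 3, substance-use row (which includes urine toxicology): weeks 0, 4, 8, 12 and 24, and follow-up weeks 4, 12 and 24. That is week 0 plus up to 7 later results.

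Two other analyses in D.12.2 do limit their data. Adherence is modelled "using 6 post-baseline time points and adherence as a continuous measure", and the viral-load model concerns "repeatedly-measured undetectable HCV VL throughout the intervention period, adjusting for substance use".

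D.11 says that baseline variables, active drug use among them, will be compared between arms, and that those found unequal will enter multivariable models.

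**The concern.** A urine sample taken before treatment cannot reflect the effect of any arm. Pooled with later samples, it pulls the arms towards each other. It is also likely to be a strong predictor of later positivity, so leaving it out of the model wastes precision and lets a chance baseline difference between arms stand in the comparison. A pooled proportion of positive person-months is not a change either, although change is what the sentence promises.

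At stake is how clearly the trial can say whether intensive care alters drug use. The protocol treats active drug use as a cause of nonadherence (B.6, D.1.6) and substance use as a potential moderator (D.10.2).

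**Working it through.** **No figure to reproduce for this analysis.** D.13 gives no power, rate, effect or correlation for drug use. As a check on the general sizing, the adherence figure can be rebuilt: 80%/80%/50% with 40 per arm, three-group chi-square, alpha 0.05 (assumed for the omnibus test). The mean rate is 0.70 and the squared deviations sum to 0.01 + 0.01 + 0.04 = 0.06. The noncentrality is 40 × 0.06 / (0.70 × 0.30) = 11.43 on 2 df, which gives 86.6% power against a stated figure above 87%. The sizing is thus an omnibus test on 40 per arm, and that n is used below.

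**Dilution.** With K post-baseline visits plus week 0, and equal arms at week 0, the expected difference is multiplied by K/(K+1).

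- K = 7: 7/8, a loss of 12.5%.
- K = 6 (no week-24 visit): 6/7, a loss of 1/7.

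**Chance imbalance at week 0.** At an assumed 50% positivity and 40 per arm, SE = √(2 × 0.25/40) = 0.112, or about 11 percentage points. A significance check at 0.05 would usually pass gaps below about 1.96 × 11.2 = 22 points.

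**Power of a valid person-level analysis (simulation).** Assumptions: week-0 positivity 50% in all arms; later positivity 30%/30%/50% (mDOT/CGT/TAU); 40 per arm; K = 7; latent-normal random intercept; two-sided 0.05; 2,000 trials per setting. The 50% and 30% are anchored loosely on the earlier cohort in D.1.3 (49% used in the 6 months before treatment, 30% during it).

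| Latent correlation | Week 0 in outcome | Post-baseline only | Post-baseline, adjusted for week 0 |
|---|---|---|---|
| 0.3 | 88% | 94% | 96% |
| 0.5 | 73% | 84% | 93% |
| 0.7 | 60% | 72% | 92% |

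Null rejection was 5.0% to 6.2% for all three. The total loss is 8, 20 and 32 points, and a repeat run gave 7, 20 and 31. Of the first set, 6, 11 and 12 points come from including week 0 and 2, 9 and 20 from not adjusting for it.

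**Cross-check by variance algebra (two arms).** For intraclass correlation r:

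- all-visit mean: effect × K/(K+1), variance factor (1 + K·r)/(K+1);
- post-baseline mean: variance factor (1 + (K−1)·r)/K;
- week-0-adjusted post-baseline mean: the previous factor minus r².

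Example with K = 7, r = 0.3 and the adjusted analysis set at 80% power: the factors are 3.1/8 = 0.3875 (all visits) and 0.40 − 0.09 = 0.31 (adjusted). The signal ratio is 0.875 × √(0.31/0.3875) = 0.783. Then 2.80 × 0.783 = 2.19, and Φ(2.19 − 1.96) = 59%, a loss of about 21 points.

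Over r = 0.05 to 0.5 the loss runs from 7.6 to 34.3 points. The extremes explored were about 2.5 points (49% v 30%, 50 per arm, K = 7, r = 0.1: 98.9% to 96.4%) and about 46 points (K = 3, r = 0.6, 80% adjusted power).

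**The planned test itself.** With no arm effect and K = 7, a three-arm chi-square on all person-months rejected in 29%, 47% and 57% of simulated trials at latent correlation 0.3, 0.6 and 0.8. With 50% v 30% it rejected in 97.8%, 95.9% and 94.8%, against 96.4%, 91.6% and 92.7% for the week-0-adjusted analysis. Its high rejection rate is not real power. The design effect is 1 + 7r, which is 1.7 to 4.5 for r = 0.1 to 0.5.

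**The case against.** The strongest reply is that the sentence names no arms and opens with the word changes. A before-versus-during comparison is a natural reading; there week 0 is the reference and nothing is diluted. Table 3 also files substance use under covariates, not outcomes. This stands in part: the documents do not say outright that week 0 is pooled as an outcome, and a reader should not take that as settled. But on the before-after reading the sentence compares no arms in a randomised trial, so it needs rewriting either way.

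A reader might also infer that the planned test loses the tabulated power. It does not. Those figures belong to an analysis that respects repeated results within a person. The chi-square as written has the opposite fault, because it rejects too often. Nor is the loss all dilution: at higher correlation, most of it comes from leaving out the covariate.

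The assumptions are thin. The D.1.3 percentages are any use over a period in one cohort without randomised arms; they are not per-visit urine positivity by arm. The calculation also holds the effect constant through follow-up, whereas in the earlier HIV DOT trial (D.1.6) adherence and viral-load differences had gone by 3 months after DOT ended. If drug-use effects fade similarly, post-treatment visits would dilute the difference too.

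Finally, D.11 could be said to deal with imbalance. It states a general rule, but a plain chi-square cannot carry a covariate, and adjustment gains precision even when the arms are balanced.

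**Conclusion.** The point holds as a low-stakes improvement. On the literal reading, week-0 urine counts as an outcome and is never adjusted for; on the other reading, no arms are compared.

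If arms are compared and week 0 is pooled, the 1/8 shrinkage (1/7 with 7 visits) is plain arithmetic. The imbalance SE of about 11 points rests on an assumed 50% positivity. The loss of about 7 to 32 points rests on assumed rates, correlation and visit count, and applies only to a valid person-level analysis; about 6 to 12 of those points are due to including week 0. The wider range of about 2.5 to 46 shows how far the answer depends on inputs that the documents do not give.

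Drug use is not among the Aim 1 hypotheses in D.12.1 and has no power claim in D.13, so the trial's main conclusions are not affected.

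**What to change.** In D.12.2, replace the person-month chi-square with the following:

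- **Contrast:** mDOT v TAU and CGT v TAU.
- **Outcome:** urine positive or negative at post-baseline visits only. Say whether the post-treatment follow-up visits count, given the possible fading noted above.
- **Model:** a per-participant GEE or mixed logistic model with arm, visit and week-0 urine result, using a missing-indicator category for a participant without a week-0 sample.
- **Report:** adjusted differences with 95% confidence intervals.

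This also deals with the correlation between results from the same person. It costs a sentence or two in the analysis plan and no new data, since the week-0 urine is already collected. If the sponsor also wants a before-after description, it can be kept as a separate, clearly labelled summary.

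### Illicit drug use is tested by chi-square on pooled person-months, which treats repeated urines from one person as independent, and the contrast is not named

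*Combined protocol and SAP*

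**What the plan says.** Section D.12.2 (analytic plan for Aim 1) states: "Changes in illicit drug use will be analyzed using urine toxicology data from each visit". It makes the person-month the unit of analysis and goes on to specify "analyzing the proportion of person-months that are positive for use of illicit drugs using a chi-square analysis". It gives no arms, periods, reference visit or significance level for this test.

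The urines are repeated within person. Section D.10.4 says: "Participants will provide urine specimens at each research visit". Table 3 lists the "Urine toxicology EMIT assay" at baseline and seven later time points (weeks 4, 8, 12 and 24, then 4, 12 and 24 weeks of follow-up). Section D.10.2 adds a visit at the end of treatment, "and then post-treatment visits after 4, 12, and 24 weeks, for a total of up to 9 research visits", which leaves up to eight after baseline. Section D.2 gives ten post-baseline visits for the 48-week regimens.

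The same section treats its other repeated outcomes differently. Of the adherence model it says: "This model accounts for within-subject longitudinal outcome correlation by taking the subject-level intercept as random". For viral load, which is also a repeated binary outcome, it says: "We will also apply mixed effects logistic regression to test the significance of mDOT and CGT on repeatedly-measured undetectable HCV VL".

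**The concern.** A Pearson chi-square assumes independent observations. Someone who uses drugs at one visit is more likely than others to be positive at the next, so pooled person-months carry less information than their number suggests when arms are compared. The p-value is then too small, and a chance difference could be reported as an effect of intensive HCV care on drug use.

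The missing contrast adds to the problem because it determines the direction of the error. The word "changes" points to a comparison over time, while the place in the Aim 1 plan points to a comparison between arms. When the same people supply both sides of a comparison, positive correlation can make the test conservative, roughly correct or liberal. The person-month unit also fits the schedule poorly, because visits stop being monthly after week 12.

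**Working it through.** The plan states no power or sample size for this analysis, so there is no figure to reproduce.

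**Inputs**
- Three arms, 1:1:1 (D.7), with 40 completers per arm (D.13).
- Post-baseline urines per person, *m*: 3 (weeks 4, 8, 12); 6 on a 12-week course if week 24 is not needed and the end-of-treatment visit coincides with week 12; 7 (Table 3); 8 (D.10.2).
- Within-person correlation *r*: not given for urines. Assumed 0.1, 0.3 and 0.5.
- Significance level: not given for this test. Assumed 5%.

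**Contrast 1: between arms (2 df, critical value 5.991)**

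The chi-square statistic is inflated by the design effect DE, so

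type I error = exp(−5.991 / (2 × DE)).

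This does not depend on the number of people. With equal correlation between all visits, DE = 1 + (m − 1)r. With decaying correlation, DE is the sum of all pairwise correlations (including each urine with itself) divided by m.

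Example: m = 7, r = 0.3 gives DE = 1 + 6 × 0.3 = 2.8 and exp(−5.991/5.6) = 0.343.

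| Urines | Structure | r = 0.1 | r = 0.3 | r = 0.5 |
|---|---|---|---|---|
| 3 | equal | 8% | 15% | 22% |
| 6 | equal | 14% | 30% | 43% |
| 7 | equal | 15% | 34% | 47% |
| 8 | equal | 17% | 38% | 51% |
| 3 | decay by visit | 7% | 13% | 20% |
| 7 | decay by visit | 8% | 17% | 29% |
| 7 | decay by calendar time | 6% | 11% | 18% |

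The last row puts the visits of a 24-week course at weeks 4, 8, 12, 24, 28, 36 and 48, and takes *r* as the correlation over four weeks. If each visit is attended with probability 80%, the 7-urine figures become about 13%, 29% and 41% (equal) and 7.5%, 15% and 25% (decay by visit).

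A beta-binomial simulation (20,000 runs, 3 × 40, 30% positive, m = 8) gave 16.6%, 38.3% and 51.9% against 17.2%, 38.0% and 51.4% from the formula. It gave 4.9% with correlation near zero.

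**Contrast 2: baseline versus k follow-up urines in the same people (1 df, critical value 3.841)**

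Ratio of true to assumed variance = Var(baseline − mean of follow-up) / (1 + 1/k), with each urine scaled to unit variance. Type I error = P(χ²₁ > 3.841 / ratio).

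- Equal correlation: the numerator is 1 + [1 + (k − 1)r]/k − 2r = (1 − r)(1 + 1/k). The ratio is 1 − r for any k, which gives 3.9%, 1.9% and 0.6%.
- Decay by visit, k = 7: ratios 0.996, 0.978 and 0.931, which give about 5.0%, 4.8% and 4.2%.
- Baseline correlates 0.1 with follow-up and follow-up urines correlate 0.5 with each other, k = 7: (1 + 4/7 − 0.2) / (8/7) = 1.20, which gives 7.4%.

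**Replacements, simulated under no effect**
- Between arms: random-intercept logistic regression 3.9% to 6.6%; GEE with robust errors 4.9% to 6.9%; ANOVA on one proportion per person 4.3% to 5.9%.
- Baseline versus follow-up: GEE with robust errors 4.5% to 5.6% in every structure tried. Random-intercept logistic regression gave 4.3% to 5.9% under equal correlation, 5.8% to 9.2% under decay by visit, and up to 17% in the 0.1/0.5 case with k = 7.
- Visit terms and a baseline covariate were not simulated.

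**The case against.** The strongest reply is that this analysis carries little weight and the size of the error is uncertain. Table 3 lists substance use among the covariates, D.12.1 has no hypothesis for it, and D.13 makes no power claim for it. The viral-load analysis already adjusts for substance use inside a mixed model. Across contrasts and assumed correlations the type I error runs from under 1% to about 50%, and no data in the documents narrow that range.

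Three narrower points also have force:
- Decay by visit number ignores the uneven visit spacing. Decay in calendar time lowers the 7-urine figures from 8%, 17% and 29% to 6%, 11% and 18%.
- The ten-visit schedule applies only to 48-week regimens. D.2 puts 100 of 150 participants on 12- to 24-week regimens, so the ten-urine result (up to 58%) is not a trial-wide figure and is left out of the table.
- The recommended model with visit terms and a baseline covariate was not itself simulated.

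These points limit the reach and the size. They do not rescue the test: every between-arm scenario still exceeds 5%, nothing elsewhere in the document supplies a clustering correction, and the contrast remains unnamed.

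**Conclusion.** The concern holds. Followed as written, the drug-use analysis gives a p-value that cannot be relied on. If arms are compared, positive within-person correlation makes the test too liberal. With three to eight urines and correlations of 0.1 to 0.5, the type I error is about 8% to 51% under equal correlation. With seven urines it is about 6% to 18% when correlation fades in calendar time. If baseline is compared with follow-up, the direction of the error cannot be known in advance, and the cases tried run from 0.6% to 7.4%. The ignored clustering and the unnamed contrast are certain from the text; the magnitudes rest on the assumed correlations and the assumed 5% level. The plan should be corrected, but the four Aim 1 outcomes and the stated power are not affected.

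**What to change.** State the contrast and the time window, then replace the chi-square with one repeated-measures method chosen in advance, modelling the urine result by visit so that the person-month unit is no longer needed.

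- **If arms are compared:** analyse the post-baseline urines with the baseline urine as a covariate. Use either the mixed-effects logistic regression already planned for viral load (subject random intercept, arm, visit) or GEE with robust errors clustered on subject. Test arm on 2 df, and state whether the two pairwise comparisons with control follow, as they do for adherence.
- **If change over time, or arm by time, is of interest:** keep baseline as a visit and test the visit or arm-by-visit term. GEE with robust errors is the safer choice here, because a random intercept alone assumes equal correlation between all visits.

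The cost is one or two sentences in D.12.2, with no new data, visits or patients.
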